**Objectives and Synopsis**

This is an open-label, multicenter pilot Phase 1 study of the checkpoint antibodies ipilimumab and nivolumab in combination with radiotherapy (RT) in 18 subjects with unresectable stage IV melanoma. All subjects will receive concurrent ipilimumab (3 mg/kg) and nivolumab (1 mg/kg) every 3 weeks for 4 doses, followed by nivolumab monotherapy (240 mg every 2 weeks). Note: per Amendment 5, nivolumab monotherapy continuing after Week 18 may be given as 480 mg every 4 weeks. Radiotherapy will be initiated after the first dose and before the second dose of immunotherapy.

There will be 2 cohorts in the study. Subjects in Cohort A will initially receive a conventional total palliative dose of 30 Gy delivered over 2 weeks in 10 fractions of 3 Gy each. Once 9 subjects have been accrued to Cohort A and completed the concurrent ipilimumab and nivolumab therapy, if  $\leq 7$  subjects have Grade 3 or 4 drug- or radiation-related adverse events, the safety of Cohort A will be deemed acceptable and additional subjects will be accrued to Cohort B (see exception in Section 3.1, i.e., asymptomatic amylase and lipase abnormalities are not included). Subjects in Cohort B will receive the high-dose hypofractionated RT for which treatment of a target lesion will comprise a total palliative dose of 27 Gy delivered over 2 weeks in 3 fractions of 9 Gy each.

The primary objective is the assessment of safety according to the National Cancer Institute (NCI) Common Terminology Criteria for Adverse Events (CTCAE), Version 4.03.

The secondary objectives are to evaluate: (1) objective response rate (ORR) at Weeks 12 and 18, (2) disease control rate (DCR) at Weeks 12 and 18, (3) duration of response, (4) progression-free survival (PFS), and (5) overall survival (OS).

The exploratory objectives are to perform correlative studies investigating the immunological effects of ipilimumab and nivolumab with RT.

Assessment methods include the NCI CTCAE (Version 4.03) for safety and the modified Response Evaluation Criteria for Solid Tumors (RECIST) 1.1 (primary) and immune-related RECIST (irRECIST; secondary) for clinical efficacy.

Sponsor: Ludwig Institute for Cancer Research, New York, NY	Study Chair: [REDACTED]
Sponsor representative Signature & Date	Study Chair Signature & Date

# 1 Background

## 1.1 Melanoma

The incidence of malignant melanoma is rising and the mortality rate is increasing.(1) These concerning trends are occurring despite the recent decline in the incidence of several other cancer types. Despite this concerning trend, the overall survival (OS) for all patients diagnosed with melanoma has improved for early stage tumors because of early detection and improved surgical treatment. Nonetheless, many patients who undergo curative-intent surgical treatment of high-risk disease ultimately recur, and recurrent and/or metastatic melanoma remains a largely fatal disease, with a median survival of 3 to 11 months.(2)

The only adjuvant treatment approved by the US FDA after resection of high-risk melanoma is IFN- $\alpha$ . Unfortunately, treatment with high-dose IFN- $\alpha$  is associated with significant side effects, and its role in prolonging survival is not clear. One study showed an OS benefit, but this was not confirmed in a pooled analysis with longer follow-up.(3, 4)

Until 2011, dacarbazine and interleukin-2 (IL-2) were the only US FDA approved treatments for metastatic melanoma. Dacarbazine provides an objective tumor response in only 5% to 20% of subjects, and these responses are short-lived (median duration of response is 6 months). Dacarbazine has also never been shown to improve OS.(2) IL-2 was approved by the FDA in 1998 for treatment of metastatic melanoma. The FDA approval was based on data suggesting a 16% overall objective response rate with a 6% complete response. However, toxicities of high dose IL-2 therapy were severe (e.g., capillary leak, sepsis, and hypotension), and 2% of subjects died from such associated adverse events (AEs).(5)

Since 2011, many new treatments have been approved for patients with melanoma. For patients with BRAF mutations, the BRAF inhibitors dabrafenib and vemurafenib have led to dramatic results with recent demonstration of an overall survival benefit of combining the BRAF inhibitor, dabrafenib with the MEK inhibitor, trametinib.(6) Immunotherapy with immune checkpoint blocking antibodies has similarly led to remarkable advances in advanced melanoma with 3 currently FDA-approved drugs: Ipilimumab, nivolumab, and pembrolizumab.(7-9)

## 1.2 Ipilimumab

Ipilimumab enhances antitumor immunity by blocking the normally negative regulator of T cell function, cytotoxic T-lymphocyte antigen 4 (CTLA-4) and has demonstrated a survival benefit for subjects with advanced melanoma in two Phase 3 trials.(10, 11) Though ipilimumab can result in impressive long-term tumor control,(12) unfortunately only a subset of patients benefit.

Responses to ipilimumab are often delayed and may be seen after initial apparent disease progression. The unique pattern of disease response seen in subjects with ipilimumab led to a retrospective study analyzing subjects treated across several Phase 2 trials.(13) In this evaluation, improved survival was associated with a variety of disease response patterns such as subjects who initially appeared to have progressive disease but later achieved response and those who had prolonged stable disease.

Though ipilimumab is generally well tolerated, a unique set of side effects, termed immune-related adverse events (irAEs) has been seen during its clinical development. The most severe

irAE is generally considered to be an inflammatory enterocolitis which requires prompt treatment with steroids and, in some cases, anti-TNF-alpha therapy. Unfortunately, a randomized trial evaluating the role of prophylactic budesonide in decreasing the rate of inflammatory colitis showed no benefit to this approach.(14) Other common severe side effects related to ipilimumab include hepatitis, dermatitis (including toxic epidermal necrolysis), neuropathy, and endocrinopathy. The following clinically significant immune-mediated adverse reactions were seen in less than 1% of ipilimumab-treated subjects in one study: nephritis, pneumonitis, meningitis, pericarditis, uveitis, iritis, and hemolytic anemia.(7)

### **1.3 Nivolumab**

Nivolumab enhances antitumor immunity by blocking another negative regulator of immunity, programmed cell death-1 (PD-1) and has demonstrated high response rates in a number of malignancies and improved OS in subjects with melanoma.(15-17) Since both ipilimumab and nivolumab act upon distinct components of the immune system, several studies are now investigating the combination of both ipilimumab and nivolumab. Impressive early efficacy was seen with an acceptable safety profile in one Phase 1 study.(18) Impressive efficacy has also been seen in phase 2 and 3 trials where the combination of nivolumab and ipilimumab was shown to improve response rates and progression free survival compared to ipilimumab alone.(19, 20)

### **1.4 Radiotherapy for Melanoma**

Radiotherapy (RT) is commonly used to palliate symptoms arising from sites of metastatic melanoma.(21) In one study, 9 of 23 subjects who received RT achieved a complete response in the irradiated area, including 3 of 23 subjects who were rendered free of disease for at least 56 months after RT.(22) RT for melanoma has also been shown to improve symptoms and prevent impending complications from metastatic disease. One prospective study evaluated palliative endpoints for 90 subjects with renal cell carcinoma and melanoma who underwent palliative RT. Improvements in two-thirds of the painful bone or soft tissue lesions were noted by investigators.(23)

The most effective dose and schedule of RT for subjects with metastatic melanoma, however, is not completely clear. In a study conducted by Overgaard et al., there was no difference in response rate between subjects receiving 5 Gy per fraction for 8 fractions versus 9 Gy per fraction for 3 fractions, though subject numbers were small.(24) In another study, Sause et al. reported the results of the Radiation Therapy Oncology Group trial 83-05, which assigned 137 subjects with melanoma to 8 Gy per fraction delivered once weekly for 4 fractions or 2.5 Gy per fraction delivered 5 days per week for 20 total fractions.(25) The response rates for both treatment arms were not statistically significantly different. These results differed slightly from a retrospective analysis of 84 subjects conducted at the Mayo Clinic, which indicated that higher doses of RT were associated with improved palliation and improved survival.(26) Importantly, dose per fraction and location of the irradiated lesions did not appear to correlate with the effectiveness of RT in this study.

It is generally believed that high-dose palliative RT is feasible for subjects with metastatic melanoma,(24) but no rigorous evaluation of dosing schemes has been tested in large, randomized studies. The dose and fractionation may have immunologic implications. Schaeue et al. found that immunologic effects and tumor control in a B16 murine melanoma model

depended upon dose and schedule of RT.(27) Tumor control was most effective and immunologic effects were most profound when RT was delivered via 7.5 Gy per fraction. In another study, when RT was delivered with anti-CTLA4 therapy, synergy was not seen when a single fraction of 20 Gy of RT was delivered.(28) A third preclinical study showed that conventionally fractionated RT abrogated the immunologic effects of RT.(29) Many radiation oncologists feel that a higher dose per fraction approach may be preferable, though prospective clinical evaluation of dose and schedule of RT in subjects with metastatic melanoma is necessary.

## 2 Study Rationale

### 2.1 Preclinical Rationale for Combining Radiotherapy and Checkpoint Blockade

To increase the numbers of subjects who benefit from ipilimumab and nivolumab, clinical trials have started combining checkpoint antibodies with other therapeutic modalities, such as chemotherapy, targeted therapy, and other immunotherapy. One additional, similarly promising approach involves combining checkpoint antibodies with RT. In a Phase 1/2 study in metastatic castration-resistant prostate cancer, ipilimumab in combination with RT demonstrated clinical antitumor activity and manageable AEs.(30) Other clinical trials exploring RT and checkpoint antibodies are ongoing.

Conceptually, all of these additional therapeutic modalities, including localized RT, could result in increased tumor destruction, releasing tumor antigens that provide further stimulus to T cells disinhibited by checkpoint blockade therapy to enhance durable antitumor immunity. It is also possible that RT may alter the tumor microenvironment and render the tumor cells more susceptible to immunologic-mediated disease regression.

In preclinical models, RT has been shown to enhance antitumor immune responses through multiple mechanisms, including increased antigen presentation in tumor draining lymph nodes and enhanced effector cell migration to the irradiated tumor.(29, 31) In one study, tumors that received RT had improved localization of inflammatory cells into the tumor microenvironment following adoptive cell transfer, which was associated with upregulation of vascular cell adhesion molecules in the tumor microvasculature that may have played a mechanistic role. RT has also been shown to increase MHC-I expression and increase the efficacy of adoptive cell transfer.(32)

In addition to RT's direct immunologic effects, preclinical evaluation has demonstrated synergy with other immunotherapeutic approaches. Specifically, when RT was combined with the immunostimulatory cytokine, FMS-like tyrosine kinase 3 (Flt3), in a lung cancer model, only mice who received RT with Flt3 had improved survival.(33) This survival was associated with the reduced development of distant pulmonary metastatic disease. A functional immune system appeared to be important as the effect was not seen in mice with deficient T cells. Regression of tumors outside of the irradiated field was also seen when Flt3 was combined with RT in a murine breast cancer model but not in mice treated with either modality alone.(34)

The immunologic effects of RT may be further enhanced by concomitant anti-CTLA-4 or anti-PD-1/PD-L1 therapy. In mouse models, CTLA-4 blockade alone resulted in no significant tumor growth inhibition, but when localized RT was administered in combination with CTLA-4 blockade, antitumor effects were seen outside of the irradiated field—a phenomenon known as the abscopal effect.(28, 35) Though the precise mechanisms involved in the abscopal effect are not completely clear, T cells appear to play a central role.(34) This phenomenon has been replicated in multiple solid tumor murine models ([name], personal communication). RT and PD-1/PD-L1 blockade have also demonstrated synergy in preclinical models.(36, 37) The triple combination of CTLA-4, PD-1, and RT has also been explored in preclinical models and suggests even greater efficacy when all three modalities are combined.(38)

## **2.2 Clinical Rationale for Combining Radiotherapy and Checkpoint Blockade**

To evaluate the potential synergy between RT and immunomodulatory therapy, Formenti et al. conducted a proof of concept study for subjects with multiple solid tumors combining RT and granulocyte-macrophage colony stimulating factor (GM-CSF). They reported that 4 of the 12 evaluable subjects (30%) experienced an abscopal response, defined as a partial response of at least 1 lesion outside of the treatment field.(39) Though subject numbers were low, recent data have additionally shown an unusually high systemic response rate when RT was combined with IL-2 therapy.(40)

Other case reports have suggested synergy between radiotherapy and immunotherapy.(41-44) Retrospective analysis of subjects treated with palliative RT during their induction course of ipilimumab at 3 mg/kg indicates that combination treatment is not associated with a higher rate of irAEs. Only one subject experienced a grade  $\geq 3$  event (diarrhea), which resolved after infliximab therapy. This side effect could have been related to ipilimumab alone.(45)

Whether the dose or schedule of RT in combination with immunotherapy is relevant remains unknown. Relatively low doses of conventionally fractionated RT (e.g., 30 Gy in 10 fractions) have been shown to be effective palliative therapy for melanoma.(23) Higher doses of hypofractionated RT (e.g., 24 Gy in 3 fractions) are also frequently used in melanoma because of perceived “radio-resistance” due to high levels of sublethal DNA damage repair in melanoma cell lines, although prospective randomized clinical studies have never confirmed this.(24)

However, the dose and fractionation of RT may have immunologic considerations relevant for its combination with immunotherapy. Preclinical studies of CTLA-4 blockade combined with RT have demonstrated the greatest delay in tumor regrowth and highest rates of complete tumor response with a dose of 24 Gy in 3 fractions (versus 20 Gy in 1 fraction or 30 Gy in 5 fractions).(28) Another study analyzing the effect of single doses of radiation from 5-15 Gy found that radiation doses of 7.5 Gy yielded the greatest proportion of tumor-reactive T cells to regulatory T cells.(27) Most importantly, these findings are consistent with our anecdotal clinical observations of abscopal effects in patients undergoing RT (both patients were treated with approximately 27 Gy in 3 fractions) during ipilimumab immunotherapy.

Additional study of the relationship between RT dose and fractionation is warranted, particularly when considering the best strategy to combine with nivolumab and ipilimumab for patients with melanoma. This information would be beneficial for subsequent studies involving combinations of nivolumab and ipilimumab in a variety of diseases and therapeutic settings.

This proposed study is therefore based upon the preclinical evidence suggesting synergy between RT and immunomodulatory therapy and early promising clinical experiences. The current study is designed to be the first prospective evaluation of the combination of ipilimumab, nivolumab, and RT.

## 3 Experimental Plan

### 3.1 Study Design

This is an open-label, multicenter pilot Phase 1 study of the checkpoint antibodies ipilimumab and nivolumab in combination with RT in 18 subjects with unresectable Stage IV melanoma. All subjects will receive concurrent ipilimumab (3 mg/kg) and nivolumab (1 mg/kg) every 3 weeks for 4 doses (Weeks 1 through 10), followed by nivolumab monotherapy (240 mg every 2 weeks) through Week 18, with optional extended treatment with nivolumab as described in Section 3.1.12. (Note: per Amendment 5, nivolumab monotherapy continuing after Week 18 may be given as 480 mg every 4 weeks, starting on Week 20, followed by Weeks 24, 28, etc.). Radiotherapy will be initiated after the first dose and before the second dose of immunotherapy.

There will be 2 cohorts in the study:

#### Cohort A:

Subjects in Cohort A will initially receive a conventional total RT palliative dose of 30 Gy delivered over 2 weeks in 10 fractions of 3 Gy each. Once 9 subjects have been accrued to Cohort A and completed the concurrent ipilimumab and nivolumab therapy, if  $\leq 7$  subjects have Grade 3 or 4 drug- or radiation-related AEs, as per Section 3.1.6, the safety of Cohort A will be deemed acceptable and additional subjects will be accrued to Cohort B.

Note: Grade 3 or 4 amylase or lipase abnormalities that are not associated with clinical symptoms will not be included in the Cohort A safety assessment described above.

#### Cohort B:

Subjects in Cohort B will receive the high-dose hypofractionated RT for which treatment of a target lesion will comprise a total palliative dose of 27 Gy delivered over 2 weeks in 3 fractions of 9 Gy each.

Radiographic imaging will be performed at Week 12 of therapy. As responses to these immunotherapeutic antibodies do not always occur at the first assessment time point and RT effects may not be apparent at the Week 12 evaluation, repeat radiographic assessment will take place after 6 additional weeks at Week 18. Subjects with symptomatic progression will be removed from the study.

#### 3.1.1 Study Phase

Pilot Phase 1

#### 3.1.2 Enrollment/Randomization

Subjects will be initially enrolled in Cohort A, with subsequent enrollment into Cohort B as outlined in Section 3.1.7. Enrollment will be under ongoing review by an internal data safety monitoring panel (see Section 3.1.14, Safety Monitoring and Study Stopping Rules).

#### 3.1.3 Blinding/Unblinding

This will be an open-label study.

### 3.1.4 Subject Population

Subjects with unresectable, stage IV metastatic melanoma are eligible for this study, as detailed further in Section 5.

### 3.1.5 Number of Sites/Subjects

This study will be conducted at 3 sites in the US, with 18 subjects estimated for enrollment.

### 3.1.6 Sample Size and Statistical Considerations

This study is intended to generate descriptive safety data. Nine subjects are anticipated for each cohort to enable a variety of disease presentations and RT targets.

Prior experience with nivolumab and ipilimumab administered in combination has been associated with a treatment-related grade 3/4 toxicity rate of 53%. A rating of Grade 3/4 drug- or radiation-related toxicity is considered to be acceptable in Cohort A if  $\leq 7$  of 9 subjects (78%) are affected (see exception in Section 3.1, i.e., asymptomatic amylase and lipase abnormalities are not included). This number was selected to avoid premature closure of exploration of this approach.

As this is the first prospective study of RT plus ipilimumab and nivolumab, no historical controls are available to anticipate the rate of toxicity of this triple combination regimen.

### 3.1.7 Treatment Arms and Treatment Schema

Table 1 presents the schedule of treatment administration.

**Table 1. Treatment Schema**

Cohort N	Week	Checkpoint Antibodies (IV)		Radiotherapy
		Ipilimumab a	Nivolumab b	
Cohort A n = 9	1	3 mg/kg	1 mg/kg	30 Gy delivered over 2 weeks in 10 fractions of 3 Gy each
	2	–	–	
	4, 7, 10	3 mg/kg	1 mg/kg	–
	12, 14, 16, 18	–	240 mg	–
	20+ b	--	240 mg Q2W or 480 mg Q4W	--
Cohort B n = 9	1	3 mg/kg	1 mg/kg	27 Gy delivered over 2 weeks in 3 fractions of 9 Gy each
	2	–	–	
	4, 7, 10	3 mg/kg	1 mg/kg	–
	12, 14, 16, 18	–	240 mg	–
	20+ b	--	240 mg Q2W or 480 mg Q4W	--

RT will be initiated after the first dose and before the second dose of immunotherapy.

Abbreviations: Gy = Gray; kg = kilogram(s); mg = milligram(s); N = number; IV = intravenously; Q2W = every 2 weeks; Q4W = every 4 weeks

a Administered once every 3 weeks for 4 doses. (3-week cycles)

b Administered once every 3 weeks for 4 doses (at 1 mg/kg) and then 240 mg once every 2 weeks.

Note: per Amendment 5, nivolumab monotherapy continuing after Week 18 may be given as 480 mg every 4 weeks, starting on Week 20, followed by Weeks 24, 28, etc.

See Section 6.1 for order of infusion.

### 3.1.8 Dosing Adjustments, Delays, and Discontinuations

Dosing adjustment, delays, and discontinuations of RT should be managed in accordance with standard of care. See Section 6.2 for administration details.

Dosing reductions in response to toxicities of ipilimumab or nivolumab are not permitted. Dosing delays and discontinuations of ipilimumab and nivolumab should be managed in accordance with Section 8.3. The following documents may also be referenced:

- YERVOY® (Ipilimumab) Package Insert: [http://packageinserts.bms.com/pi/pi\\_yervoy.pdf](http://packageinserts.bms.com/pi/pi_yervoy.pdf)
- YERVOY® (Ipilimumab) Immune-mediated Adverse Reaction Management Guide: <https://www.hcp.yervoy.com/pages/remms.aspx>
- Opdivo® (Nivolumab) Package Insert: [http://packageinserts.bms.com/pi/pi\\_opdivo.pdf](http://packageinserts.bms.com/pi/pi_opdivo.pdf)
- Management Algorithms for Adverse Events Associated with Immuno-oncology Agents (see Section 8.3.1).

Note: As durable disease stabilization and/or objective tumor response may be observed after early progression, it is recommended that, in the absence of toxicity requiring discontinuation in accordance with the package insert, all 4 doses of concurrent ipilimumab and nivolumab be administered over the initial 12 weeks, even in the setting of apparent clinical progression, provided the subject's performance status remains stable.

Even in the event of a dose delay, disease assessments should be performed according to standard of care on the originally scheduled study days.

Dose modifications for radiotherapy as a result of toxicity are allowed per the Investigator's assessment.

### 3.1.9 Dose-limiting Toxicity

The DLT and MTD will not be defined or determined. A safety review will be conducted when 9 subjects have been accrued to Cohort A and completed the concurrent ipilimumab and nivolumab therapy. If  $\leq 7$  subjects have Grade 3 or 4 drug- or radiation-related AEs, the safety of Cohort A will be deemed acceptable and additional subjects will be accrued to Cohort B. The Cohort A assessment period for this evaluation will include the first 2 cycles of treatment, up to and including the pre-dose safety assessments scheduled for Cycle 3 (see Section 4.1.2).

Note: Grade 3 or 4 amylase or lipase abnormalities that are not associated with clinical symptoms will not be included in the Cohort A safety assessment described above.

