### **3.1.13 Interim Analysis**

An interim analysis of safety will be performed after 9 subjects in Cohort A have completed concurrent ipilimumab and nivolumab therapy in order to determine whether to proceed with enrollment into Cohort B (see Section 3.1).

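### The at-most-7-of-9 rule can serve as a lenient gate to Cohort B, but passing it cannot support the conclusion that Cohort A safety is acceptable

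*Combined protocol and SAP*

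**What the plan says.** Section 3.1.9 sets the timing: "A safety review will be conducted when 9 subjects have been accrued to Cohort A" and those subjects have finished the concurrent antibody phase. The count itself covers the first two cycles, up to the pre-dose assessments for Cycle 3, and leaves out asymptomatic Grade 3/4 amylase and lipase abnormalities. If the count is 7 or fewer, two things follow in one sentence: "the safety of Cohort A will be deemed acceptable and additional subjects will be accrued to Cohort B". The Synopsis and Section 3.1 give the same two consequences.

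Section 3.1.6 also calls the toxicity acceptable if at most 7 "of 9 subjects (78%) are affected". It gives one benchmark: the two antibodies without radiotherapy, a combination that "has been associated with a treatment-related grade 3/4 toxicity rate of 53" per cent. It explains the cutoff candidly: "This number was selected to avoid premature closure of exploration of this approach". It describes the study as descriptive and says that no historical controls exist for the triple regimen.

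Section 3.1.13 gives the purpose of the interim look: "in order to determine whether to proceed with enrollment into Cohort B". Section 4.1.2 plans descriptive adverse-event summaries on the ITT population for both cohorts, with no interval for any safety rate. Section 4.2.2, by contrast, plans 95% binomial intervals for tumour response. The plan states no pass probability for the 7-of-9 rule.

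**The concern.** Safety is the primary objective, and this is the only count-based rule that turns safety data into a stated conclusion. The rule does two jobs. It decides whether to open Cohort B, and it labels Cohort A safety as acceptable. The reason given in Section 3.1.6, avoiding early closure, supports only the first job.

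If the label stands, the report can say that Cohort A met its prespecified criterion for acceptable safety when the data are compatible with nearly every subject having a Grade 3/4 related event. A reader of the primary result would take the pass as evidence about the toxicity rate, and nine subjects give very little of that.

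**Working it through.** **Inputs.** n = 9 and a pass at 7 or fewer (Section 3.1.9); limit printed as 78% and benchmark of 53% (Section 3.1.6).

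**The plan's own figure.** 7/9 = 0.778, which rounds to the printed 78%.

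**Pass probability.** Let X be the number of the 9 subjects with a counted event. Take subjects as independent with a common true rate p. Only 8 or 9 events fail, so

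P(pass) = P(X ≤ 7) = 1 − 9p⁸(1 − p) − p⁹.

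At p = 0.70: p⁸ = 0.0576 and p⁹ = 0.0404, so P(pass) = 1 − 9 × 0.0576 × 0.30 − 0.0404 = 0.804.

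| True rate p | P(pass) |
|---|---|
| 53% | 97.0% |
| 60% | 93.0% |
| 70% | 80.4% |
| 77.8% (7/9) | 62.8% |
| 80% | 56.4% |
| 85% | 40.1% |
| 90% | 22.5% |
| 95% | 7.1% |

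Solving the formula for p, failing becomes likelier than passing only above a true rate of about 82%. The rule fails 90% of the time only above about 94%.

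**What a passing count says about the rate.** Exact (Clopper-Pearson) 95% limits for x of 9 are the 0.025 quantile of Beta(x, 10 − x) and the 0.975 quantile of Beta(x + 1, 9 − x).

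| Observed | Exact 95% CI |
|---|---|
| 4/9 | 13.7% to 78.8% |
| 5/9 | 21.2% to 86.3% |
| 6/9 | 29.9% to 92.5% |
| 7/9 | 40.0% to 97.2% |

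Each passing count from 4 to 7 leaves an upper limit above 78%.

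**Sensitivity to the window.** The rule counts two of the four concurrent cycles. The documents do not give the period behind the 53%. Assume that 50% to 80% of those events fall within two cycles. The benchmark rate in the window is then 0.53 × 0.5 = 0.265 to 0.53 × 0.8 = 0.424, and P(pass) is 99.98% to 99.4%. Leaving out asymptomatic amylase and lipase events works in the same direction. Section 3.1.11 works slightly the other way: a subject with an event always counts, while an event-free subject outside the per-protocol population is replaced. The binomial ignores this.

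**The case against.** The strongest defence is that the rule is a gate and behaves like one. Passing 97% of the time at the 53% benchmark is what a gate should do if radiotherapy adds nothing. Passing 63% of the time at 78% follows from putting the cutoff there. The leniency is disclosed, the study is descriptive, and the overall safety analysis in Section 4.1.2 is separate from the rule. Read with Section 3.1.13, acceptable could mean acceptable to proceed. All of this stands as a defence of the gate.

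It does not rescue the label. Section 3.1.9 states acceptability and accrual as two consequences, and Section 3.1.6 attaches the word to the toxicity itself without mentioning the decision to proceed.

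Four stronger readings are tempting, and the documents do not support them:

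- **The cutoff should be lower.** With n = 9, a cutoff of 6 passes 87.7% of the time at 53% and 32.2% at 7/9; a cutoff of 5 passes 68.4% and 11.8%. No cutoff both passes reliably at 53% and fails reliably at 78%. The limit is the size of the pilot.
- **The word acceptable should need a stricter count.** Requiring a one-sided 95% upper limit below 78% means at most 4 of 9 (upper limit 74.9%, against 83.1% at 5 of 9). That sits below the 53% benchmark and would be met only 43% of the time at a true rate of 53%. Nothing in the plan calls for such a bar.
- **The rule is a weak hypothesis test.** The plan states no null rate, alpha or power.
- **Cohort B opens with no one looking.** Section 3.1.9 requires a safety review, and Sections 3.1.2, 3.1.14 and 4.1 provide continuing panel oversight. Section 3.1.14 allows suspension at any count. It is true that Cohort B has no numeric rule, but there is no later cohort for it to gate.

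**Conclusion.** The point holds for the conclusion drawn from a pass, not for the decision to proceed. At true rates above the plan's own 78% limit, the rule is still passed 56% of the time at 80%, 40% at 85% and 23% at 90%. A pass at the limit is compatible with a true rate anywhere from 40% to 97%. So a pass does not show that the Grade 3/4 related-event rate is at or below 78%, and it says little about whether radiotherapy adds toxicity to the 53% benchmark.

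The pass probabilities assume independent subjects, one common rate, and a true rate that refers to the two-cycle window with the stated exclusions. If the 53% comes from a longer period, passing is more likely still at the benchmark. Whether 7 of 9 is the right clinical limit is outside this point.

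**What to change.** 1. In the Synopsis and Sections 3.1, 3.1.6 and 3.1.9, keep the threshold of 7 of 9 and replace the acceptability wording with a statement that accrual to Cohort B may proceed.
2. In Section 3.1.6, add the pass probabilities for a range of true rates, with the window assumption, and state that passing does not show a rate at or below 78%.
3. In Section 4.1.2, add the proportion of subjects with at least one Grade 3/4 related event, with an exact 95% confidence interval, for each cohort. Name the period covered and say whether asymptomatic amylase and lipase abnormalities count. Base any statement about safety on that interval. This matches what Section 4.2.2 already does for response.

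The cost is wording in four places, a short table and one interval per cohort, with no extra subjects. The real downside is a less favourable stated conclusion: Cohort A could pass the gate and still be reported with a wide interval and no verdict. No new cutoff, added review step or hypothesis test is needed.
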